3.9. Patient-reported endpoint evaluation

3.9.1. Patient-reported endpoints

Patient reported outcomes of disease/treatment-related symptoms, patient functioning, and HRQoL will be assessed using the EORTC QLQ-C30 and the modified QLQ-BR23 (Aaronson et al. 1993) for all randomized patients. Hence, patient-reported endpoints are the mean and mean change scores (of the base questionnaire and of the supplementary breast cancer module) of the scales, which are described in the scoring procedures (Fayers et al. 2001).

3.9.2. Analysis for patient-reported endpoints

Completion rates of the measures will be summarized at each time point by treatment arm.

The population for analysis will be defined as all randomized patients who have completed baseline and at least one post-baseline assessment. Summary statistics (mean, mean change, standard deviation, median and 95% CI) of linear transformed scores will be reported for all subscales of the EORTC QLQ-C30 questionnaire, and the modified QLQ-BR23 (including the added items of skin problems, itching, sore mouth/tongue, and trouble swallowing, which will be assessed independently). Both measures and additional scales from the EORTC item bank will be scored according to the EORTC scoring manual guidelines (Fayers et al., 2001). Line charts depicting the mean changes (and standard errors) of items and subscales over time will be provided for each treatment arm from the baseline assessment. Clinically meaningful differences will be assessed relative to established thresholds (Osoba et al., 1998; Cocks et al., 2011).

Additional patient reported outcomes analyses might be conducted.

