2.1.4. Patient-reported outcome objectives

The patient-reported outcome (PRO) objectives for this study are as follows:

- Evaluate and compare PROs of treatment-related symptoms, patient functioning, and health-related quality of life (HRQoL), including side-effects of therapy (e.g., sore mouth/tongue, difficulty swallowing, diarrhea, skin problems), between treatment arms as measured by the European Organisation for Research and Treatment of Cancer (EORTC) Quality of Life Questionnaire Core 30 (QLQ-C30) and the modified Breast Cancer Module (QLQ-BR23)

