3.1.2. Missing data

Subjects may have missing specific data points for a variety of causes. In general, data may be missing due to a missed visit, non-evaluability of a specific clinical measurement at its planned clinical visit or a subject's early withdrawal from study. The general procedures outlined below describe what will be done when a data point is missing.

3.1.2.1. *Imputations of missing data*

Generally, only evaluable measurements are considered for the analyses. No values are imputed for missed or non-evaluable visits. In case of primary and secondary efficacy endpoints possible specific requirements are stated in the according analysis sections.

3.1.2.2. *Partial dates*

Partially incomplete dates (day or day/month missing) will be imputed for dates related to AEs, to concomitant medication and medical history. Completely missing dates and missing years will not be imputed.

For DOB imputed dates will be used to derive the age of the patients since only month and year are captured due to regulatory reasons in some participating countries. DOB must not

have missing month information and hence, missing months will not be imputed. DOB will be imputed as described in the following table:

	Missing	Impute	Exception
DOB	Day	15	--

Dates belonging to AEs and concomitant medication will be imputed as described in the following table:

	Missing	Impute	Exception
Start date	Day	01	Date of first dose of study drug if imputed date would be prior to date of first dose of study drug
	Day/Month	01JAN	Date of first dose of study drug if imputed date would be prior to date of first dose of study drug
Stop date	Day	Last day of the month	Patient EOS date if the imputed date would be after patient EOS date
	Day/Month	31DEC	

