3.3. Analysis populations

3.3.1. Intention-to-Treat population

Primary and secondary analyses, as well as patient-reported and exploratory analyses, will include the Intention-to-Treat (ITT) population; that is, all patients who were randomized regardless of whether they received any study drug (GDC-0032 or placebo). Patients will be analyzed according to the treatment group to which they were assigned at randomization.

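### Patient-reported outcomes: section 3.9.2 narrows the population set in 3.3.1 and 3.9.1, and plans no between-arm estimate that allows for missing questionnaires

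*SAP*

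**What the plan says.** Three sections of the SAP bear on who is analysed.

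- Section 3.3.1: "Primary and secondary analyses, as well as patient-reported and exploratory analyses, will include the Intention-to-Treat (ITT) population", which it defines as everyone randomized, treated or not.
- Section 3.9.1 has the questionnaires assessed with the EORTC QLQ-C30 and the "modified QLQ-BR23 (Aaronson et al. 1993) for all randomized patients".
- Section 3.9.2: "The population for analysis will be defined as all randomized patients who have completed baseline and at least one post-baseline assessment".

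On purpose, 2.1.4 sets out to "Evaluate and compare PROs of treatment-related symptoms, patient functioning, and health-related quality of life (HRQoL), including side-effects of therapy", between treatment arms.

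On method, 3.9.2 says "Summary statistics (mean, mean change, standard deviation, median and 95% CI) of linear transformed scores will be reported" and "Line charts depicting the mean changes (and standard errors) of items and subscales over time will be provided for each treatment arm". It also plans completion rates by visit and arm, a reading against published thresholds for meaningful differences, and leaves room for further analyses without naming any.

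On missing data, 3.1.2.1 says "No values are imputed for missed or non-evaluable visits". Its only exception is this: "In case of primary and secondary efficacy endpoints possible specific requirements are stated in the according analysis sections". Patient-reported outcomes are not covered by it.

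**The concern.** There are two separate defects.

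First, the population is stated in two ways. An analyst following 3.3.1 and one following 3.9.2 could report different denominators, and section 4, which lists changes of analysis, does not mention the point.

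Second, the objective promises a comparison, but the plan contains no between-arm quantity. Readers will form the comparison themselves by subtracting one arm's mean from the other's at each visit, and 3.9.2 invites this by referring to meaningful differences. Those means rest on whoever answered at that visit. The symptoms named in 2.1.4 (sore mouth, difficulty swallowing, diarrhea, skin problems) are ones that could plausibly affect whether a patient keeps answering. If they do so unevenly by arm, the later-visit contrast is distorted, and nothing in the plan would adjust it.

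**Working it through.** The SAP states no sample size, effect or dropout rate for patient-reported outcomes, so there is no figure of its own to reproduce. Every numerical input below is an assumption, apart from 165 per arm, which is the planned 330 split 1:1 (330 / 2).

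**1. Size and sign of the bias at one visit.** Let w be the share of an arm with no score at that visit, and D how many points worse those patients are than the responders. The bias in the observed-only difference, in favour of GDC-0032, is

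bias = wG × DG − wP × DP.

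With placebo non-response at 5% and equal D in both arms:

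| GDC-0032 non-response | D = 10 | D = 30 |
|---|---|---|
| 10% | 1.0 − 0.5 = 0.5 | 3.0 − 1.5 = 1.5 |
| 15% | 1.5 − 0.5 = 1.0 | 4.5 − 1.5 = 3.0 |
| 25% | 2.5 − 0.5 = 2.0 | 7.5 − 1.5 = 6.0 |

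The bias is zero if D = 0, or if w and D are the same in both arms. It reverses if placebo leavers are worse off: with 10% non-response in each arm, D = 5 on GDC-0032 and D = 20 on placebo, it is 0.5 − 2.0 = −1.5. A 5-point bias needs GDC-0032 non-response of 5/20 + 0.05 = 30% at D = 20, or 5/30 + 0.05 = about 22% at D = 30.

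**2. Simulation of one symptom item.** Inputs: 165 per arm, five visits, baseline mean 20, SD 20, common correlation 0.4; 25% of GDC-0032 and 5% of placebo patients worsen; a 40% chance of leaving after an observed score above 60. The true difference in mean change should be near (0.25 − 0.05) × worsening, that is 8 points for a 40-point worsening and 6 for 30.

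| Worsening | Timing | True | Observed-case | Shortfall |
|---|---|---|---|---|
| 40 points | from first post-baseline visit | 8.06 | 5.14 | 2.92 / 8.06 = 36% |
| 40 points | builds up linearly | 8.2 | 7.1 | 1.1 / 8.2 = 13% |
| 30 points | from first post-baseline visit | 5.96 | 4.68 | 1.28 / 5.96 = 21% |
| 30 points | builds up linearly | 6.1 | 5.7 | 0.4 / 6.1 = 7% |

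The result also depends on the assumed baseline mean. In the immediate 40-point case, means of 25 and 30 give observed-case differences of 4.7 and 4.0 against a true value of about 8, so larger shortfalls.

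A likelihood-type estimate that uses all earlier scores gives 7.77 and 5.86 in the two immediate cases. That recovery is built in, because leaving was made to depend only on observed scores.

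**3. How much comes from the population rule.** In this set-up only about 1% of each arm lacks a post-baseline score, equally in both arms. A patient who leaves after a high post-baseline score already meets the 3.9.2 criterion and stays in the set. The shortfall therefore comes almost wholly from missing later visits.

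**The case against.** The strongest case against has four parts.

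- **Direction.** A reader might infer that the plan will make GDC-0032 look better tolerated than it is. The SAP does not support that. It gives no withdrawal rate, no difference between arms and no scores for leavers. Section 2.2 also describes another way out of the study, for patients with progression, which could be commoner on placebo. This objection stands.
- **Who is excluded.** A reader might also infer that 3.9.2 removes everyone who leaves early. It removes only those without a baseline or without any later questionnaire. Section 3.1.4 also keeps early end of treatment separate from early end of study, so stopping the drug need not mean an end to questionnaires. The questionnaire schedule is not in the SAP and may be in the protocol, so the extent of loss cannot be judged here. This stands too.
- **Safeguards.** Completion rates by visit and arm (3.9.2) and discontinuations with reasons (3.5.1, 3.5.4) are planned. Tolerability is assessed through adverse events in all treated patients (3.3.3, 3.8.2), so it does not rest on questionnaires alone. This limits the consequence, but these tables would show selective non-response without correcting for it.
- **Descriptive by choice.** These outcomes are neither primary nor secondary efficacy endpoints, and no test is planned, so descriptive summaries are legitimate. A model for every scale adds many unadjusted intervals. That is a reason to make the added analysis supportive, not to omit it when the stated objective is a comparison.

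One could also read 3.9.2 as a specific rule that overrides the general one. The SAP does not say so, and 3.9.1, in the same chapter, again refers to all randomized patients.

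**Conclusion.** The point holds on the text: the population is inconsistent between 3.3.1/3.9.1 and 3.9.2, and the comparison promised in 2.1.4 has no planned between-arm estimate and no allowance for missing questionnaires.

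The bias is a possibility, not a demonstrated result. Under the simulated inputs, with baseline mean 20, the observed-case difference is about 7% to 36% too small, depending on the size and timing of the worsening. Under other inputs it could be larger, nil or reversed. The population wording needs correcting for consistency, but it contributes almost nothing to that shortfall. The change is worth making because it is cheap and supplies the comparison the SAP sets as its objective. It does not affect the primary analyses.

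**What to change.** 1. Name one patient-reported population in 3.3.1, 3.9.1 and 3.9.2: all randomized patients with at least one questionnaire, analysed as randomized.
2. Keep the descriptive tables, completion rates and line charts.
3. Add to 3.9.2, for each scale, a supportive mixed model for repeated measures with baseline as part of the response vector (so that patients with only a baseline stay in), and with arm, visit, arm-by-visit, tumor size and nodal status. Report the between-arm difference with 95% CI at each visit.
4. Label these intervals as descriptive, without multiplicity control.
5. Add one sensitivity analysis for missingness that depends on unobserved scores, for example delta-adjusted imputation.

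Cost: SAP wording and a little more analysis work in standard software, on data already collected. The main model assumes that missingness depends only on observed data (item 5 probes this), and the report will carry many unadjusted intervals.

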3.10. Exploratory endpoint evaluation

Details on evaluation (endpoints and analyses) of all translational science objectives will be described in the Translational Statistical Analysis Plan (TSAP). Analyses will include pharmacodynamics and pharmacokinetic, as well as biomarker endpoint evaluation.

3.10.1. Exploratory endpoints

ORR (centrally assessed, ICON: dataset RVIS, variable RRESPONS – CR, PR, SD, Non-CR/Non-PD, PD, NE, ND), pCR rate (local, tpCR - yes, no, not assessed), PEPI score (derived – classified into risk groups according to Ellis et al 2008 as PEPIR and PEPIB, respectively) according to the decrease in Ki67 after 2 weeks of treatment are hypothesized to differ between patients receiving letrozole plus GDC-0032 compared to patients receiving letrozole plus placebo. Each will be evaluated in all randomized patients and, if statistically significant within all randomized patients, also in PIK3CA MT patients.

The concordance of the different imaging modalities in measuring tumor response after completion of study drug (MRI, central, ICON: dataset RVIS, variable RRESPONS – CR, PR, SD, Non-CR/Non-PD, PD, NE, ND; clinical, ultrasound and mammography, local, OverResp for each - CR, PR, SD, PD, not measurable/not assessed) will be observed. Concordance will be evaluated in all randomized patients.

Rates of planned BCS (local, SurgTypePlan - breast conserving, other levels) and conversion to BCS (local, SurgType - breast conserving, other levels) between patients receiving letrozole plus GDC-0032 and patients receiving letrozole plus placebo will be compared. Rates will be evaluated in all randomized patients.

3.10.2. Analysis for exploratory endpoints

Comparisons between treatment arms in ORR (grouped as responder vs. non-responder), pCR rate and PEPI score according to the decrease in Ki67 will be analyzed using appropriate regression analysis models (depending on the distribution of the variables), e.g. logistic regression models, adjusting for tumor size and nodal status in all randomized population and in PIK3CA MT population. Concordance will be examined by frequencies and percentages. Rates will be summarized descriptively.

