2.1.5. Exploratory objectives

The exploratory objectives for this study are as follows:

- ORR, pCR rate, and PEPI scores according to the decrease in Ki67 after 2 weeks of letrozole plus GDC-0032 and letrozole plus placebo.
- To evaluate changes in tumor cellular composition as assessed by diffusion-weighted MRI
- To assess whether biomarkers from tumor tissue or blood, including but not limited to somatic cancer associated mutations, phosphatase tensin homolog (PTEN) expression, pro-survival pathways (such as phosphatidylinositol-3-kinase (PI3K)/AKT, mitogen-activated protein kinase (MAPK) etc.), apoptotic markers, hormone receptor expression levels, and levels of RNA and DNA expression are predictive of response
- To determine whether inhibition of PI3K with GDC-0032 results in changes in downstream markers in tumor tissue and to examine the relationship to anti-tumor activity
- To assess concordance and percentage of PIK3CA mutation status from baseline biopsy and surgical specimen
- To assess emergence of resistance alleles from tumor tissue or blood

- To assess concordance of the different imaging modalities (MRI [volume, enhancement, diffusion metrics], ultrasound, mammography) in measuring tumor response
- To assess the pharmacokinetics and possible drug interaction between letrozole and GDC-0032 upon concomitant administration
- To assess the correlation of GDC-0032 drug levels and GDC-0032 related response (efficacy or AEs [e.g., colitis, rash])
- To assess the influence of pharmacogenetic polymorphisms on GDC-0032 and/or letrozole on pharmacokinetics (e.g. drug metabolizing enzymes and transporters) and response (either efficacy and/or AEs)
- Compare the rates of breast-conserving surgery (BCS) and conversion to BCS in letrozole plus GDC-0032 versus letrozole plus placebo

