2.4. Number of subjects - sample size estimation

This study is designed for testing the effect of GDC-0032 on the two co-primary endpoints in all enrolled patients and in the PIK3CA MT patients and plans to enroll 330 patients in total. Assuming the PIK3CA mutation status will not be available (unknown) for approximately 10% of the patients and the prevalence of PIK3CA MT is 40%, there will be approximately 120 patients in the PIK3CA MT cohort.

Given that the PIK3CA mutation status is not a stratification factor for randomization, there might be a possible imbalance between treatment arms within the PIK3CA MT cohort, which may reduce the statistical power in this cohort. To ensure the study provides sufficient statistical power even when the treatment assignment is imbalanced, the sample size was calculated based on a conservative scenario by assuming that the treatment assignment imbalance in PIK3CA MT is 40% vs. 60%. The sample size was calculated based on a χ^2 -test using continuity correction (Ury and Fleiss 1980).

To control an overall, two-sided, family-wise error rate under 20% for each analysis population, we use a two-sided significance level of 16% and 4% for the co-primary endpoints MRI ORR, and pCR, respectively.

Assuming 10% of the patients are unevaluable for the MRI ORR, approximately 300 enrolled patients and 108 patients in the PIK3CA MT cohort will be evaluable for analyses. This sample size allows us to detect an absolute percentage increase of 24% in MRI ORR rate in the letrozole plus GDC-0032 arm (64%) versus the letrozole plus placebo arm (40%; Smith et al. 2005; Ellis and Ma 2007) in the PIK3CA MT cohort at 80% power and 16% two-sided significance level. The minimal detectable difference for ORR is approximately 15%.

Assuming that all patients are evaluable for pCR (i.e., approximately 330 enrolled patients and 120 in the PIK3CA MT cohort), this sample size provides 80% power to detect an absolute percentage increase of 18% in pCR in the letrozole plus GDC-0032 arm (19%) versus the letrozole-only arm (1%, Smith et al. 2005; Ellis and Ma 2007) in the PIK3CA MT cohort at the 4% two-sided significance level. The minimal detectable difference for pCR rate is approximately 13%.

The study is considered positive if at least one population shows a statistically significant result regarding the co-primary endpoints.

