3.7. Secondary endpoint evaluation

3.7.1. Secondary endpoints

As secondary efficacy endpoints (1) tumor ORR (ICON: dataset RVIS, variable RRESPONS – CR, PR, SD, Non-CR/Non-PD, PD, NE, ND), centrally assessed by modified RECIST 1.1 criteria by breast MRI after completion of study drug, and (2) the rate of total pCR (tpCR - yes, no, not assessed) in breast and axilla, locally evaluated after completion of study drug and surgery, both are evaluated in PIK3CA WT patients.

Furthermore, secondary efficacy endpoints contain tumor overall ORR (CR, PR, SD, PD, not measurable/not assessed), locally assessed by modified RECIST 1.1 criteria by clinical breast examination (CaPalpOverResp), mammography (CaMammoOverResp), and breast ultrasound (CaSonoOverResp), after completion of study drug evaluated in all randomized patients and separately by PIK3CA mutation status.

Additionally, (1) change in Ki67 values (VHIO: variable Ki67ResN), centrally assessed, from baseline to Week 3, baseline to surgery, and Week 3 to surgery, (2) PEPI score (for relapse-free survival and breast cancer-specific survival, derived – classified into risk groups according to Ellis et al 2008 as PEPIR and PEPIB, respectively), at surgery, and (3) change in enhancing tumor volume (ICON: dataset VLES, variable TSHOLD1 - metric), centrally evaluated using breast MRI, from baseline to surgery, are considered as secondary efficacy endpoints in all randomized patients and in each of the PIK3CA mutation cohorts.

Last, different definitions of pCR, locally assessed after completion of study drug and surgery, are evaluated in all randomized patients and in each of the PIK3CA mutation cohorts. Included are the following possibilities: a) ypT0, ypN0 (according levels for

ypTStage and ypNStage), and b) ypT0/is, ypNX (breast pCR as nodal stage is not considered; bpCR - yes, no, not assessed).

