Target lesions should be selected on the basis of their size (lesions with the longest diameter) and should lend themselves to reproducible repeated measurements. Up to 2 lesions in the breast may be identified as target lesions. A sum of the diameters of all target lesions will be calculated and reported as the baseline sum of diameters. The baseline sum of diameters will be used as a reference to further characterize any objective tumor regression in the measurable dimension of the disease. Lesions that meet the criteria for radiographically defined simple cysts should not be considered malignant lesions (neither target nor non-target) since they are, by definition, simple cysts. Pathologic axillary lymph nodes are not to be designated as target lesions, and lymph node measurements are not to be included in the sum of diameters (see below for more detail).

Bilateral breast imaging studies should be conducted at each study assessment. The same method of measurement and the same technique should be used to characterize each target lesion at baseline and during the study, and all measurements should be recorded in metric notation. Care must be taken in measurement of target lesions with different modalities, since the same lesion may appear to have a different size with each modality. If for some reason the same imaging modality cannot be used at a scheduled assessment time point, then the case should be discussed with the radiologist to determine if substitution of any other approach is possible and, if not, the patient should be considered not evaluable at that time point, for that particular type of imaging assessment.

Non-Target Lesions

Non-target lesions may include any other measurable breast lesions not identified as target lesions, as well as truly non-measurable lesions, such as diffuse skin thickening or other lesions not measurable by reproducible imaging techniques.

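### Imaging concordance is planned only as raw percentages of response categories, without chance correction, a category mapping or any use of the recorded tumor measurements

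*SAP*

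**What the plan says.** SAP 2.1.5 sets the objective: "To assess concordance of the different imaging modalities (MRI [volume, enhancement, diffusion metrics], ultrasound, mammography) in measuring tumor response".

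SAP 3.10.1 turns it into an endpoint: "The concordance of the different imaging modalities in measuring tumor response after completion of study drug". For central MRI the variable is the overall response RRESPONS, with levels CR, PR, SD, Non-CR/Non-PD, PD, NE and ND. For clinical examination, ultrasound and mammography it is "OverResp for each - CR, PR, SD, PD, not measurable/not assessed". The population is all randomized patients. MRI volume, enhancement and diffusion do not appear in the concordance endpoint.

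SAP 3.10.2 gives the method in one sentence: "Concordance will be examined by frequencies and percentages". It names no agreement index, confidence interval or rule for the levels that exist on one side only.

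Measured data exist. In Appendix 1 (Target Lesions), "A sum of the diameters of all target lesions will be calculated and reported as the baseline sum of diameters", and "all measurements should be recorded in metric notation". Appendix 1 applies its response criteria to ultrasound, mammography and clinical examination as well as MRI. Section 3.7.1 already holds "change in enhancing tumor volume (ICON: dataset VLES, variable TSHOLD1 - metric") as a secondary endpoint.

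**The concern.** The objective asks how well the modalities agree in measuring response. The planned output answers a narrower question, and in a form that is hard to interpret, for four reasons.

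- **Chance.** Most patients are expected to be PR or SD, so a sizeable raw agreement arises even between unrelated readings. A percentage alone does not show how much of it is real.
- **The 30% cut.** It splits near-identical readings and merges very different ones. A systematic over- or under-measurement against MRI is not estimated.
- **Category sets.** MRI has Non-CR/Non-PD, NE and ND; the local reads have one combined level for not measurable or not assessed. Whether NE against not assessed counts as agreement, disagreement or neither is left open, and the percentage depends on it.
- **Scope.** The MRI metrics named in the objective are dropped from the concordance endpoint without a stated reason.

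At stake is whether the trial can say how far ultrasound, mammography or palpation can stand in for MRI.

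**Working it through.** **1. Figures in the plan.** The SAP gives no figure for concordance, so there is none to reproduce. The response rates used below are the design rates in 2.4: 40% and 64% for MRI ORR in the PIK3CA MT cohort. They are read correctly: two-sided 16%, 80% power, 40:60 allocation and continuity correction return 108 evaluable patients, as stated (90 without the correction). Applying these rates to all randomized patients is an assumption.

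**2. Agreement expected by chance.** With equal marginals p1, p2, ... for two unrelated modalities, Pe is the sum of the squared marginals.
- Responder or not, at the mean rate (40 + 64)/2 = 52%: Pe = 0.52² + 0.48² = 0.2704 + 0.2304 = 0.50.
- Four categories, assumed CR 5, PR 47, SD 43, PD 5%: Pe = 0.0025 + 0.2209 + 0.1849 + 0.0025 = 0.41.
- Range over assumed mixes: CR 15, PR 37, SD 43, PD 5% gives 0.35; CR 0, PR 52, SD 48, PD 0% gives 0.50.

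**3. Effect on interpretation.** Kappa = (Po − Pe)/(1 − Pe). On responder status with Pe = 0.50, raw agreement of 75% is kappa 0.25/0.50 = 0.50, and 85% is 0.35/0.50 = 0.70. With 297 patients the 95% CI half-width for raw agreement of 65-85% is about 4 to 5 points, so precision is not the obstacle.

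**4. Effect of the cut.** Appendix 1 sets PR at a decrease of at least 30% in the sum of diameters. With no non-target or new lesions, shrinkage of 29% on one modality and 31% on another is SD against PR (discordant, 2 points apart), while 31% and 90% is PR against PR (concordant, 59 points apart).

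**5. Structural discordance.** SAP 3.1.4 says that PR is not possible where only non-target lesions were documented at screening, and that this may occur on clinical examination, mammography or ultrasound but should not on MRI. Such a modality can yield CR, SD, PD or NE. If MRI gives PR, the pair is discordant whatever was seen.

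**6. Illustration of the information lost.** Normally distributed percent change was simulated for MRI and two local modalities and cut at the 5th, 52nd and 95th percentiles. Power at two-sided 5% to show that one tracks MRI better: McNemar on agreement with MRI (categories) against Steiger's test for dependent correlations (percent change). The correlation between the local modalities was 0.45-0.65.

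| Assumed correlations with MRI | Categories, n=300 | Percent change, n=300 | Categories, n=200 | Percent change, n=200 |
|---|---|---|---|---|
| 0.8 vs 0.7 | 43% | 95% | 31% | 82% |
| 0.75 vs 0.65 | 34% | 86% | 24% | 68% |
| 0.7 vs 0.6 | 28% | 76% | 19% | 59% |
| 0.6 vs 0.5 | 19% | 57% | 15% | 41% |

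If the local modalities are independent given MRI, the n=300 figures are 39, 32, 24 and 16% against 92, 81, 64 and 48%. For wider gaps, on responder status with 297 patients, categories do better: 61% for 0.7 vs 0.5 and 78% for 0.8 vs 0.6.

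**The case against.** Overall response is a legitimate measure of tumor response; it defines the ORR endpoints in 3.6.1 and 3.7.1. It also carries information that diameters do not. In Table 1 of Appendix 1, a target CR with persisting non-target disease becomes PR, and a new lesion or non-target progression gives PD whatever the diameters show. Nodes are never in the sum. A reader might infer that every category is simply a cut of percent change; Table 1 contradicts that. The simulation makes exactly this simplification, so in it categories can only lose information. This stands, and is why the category tables should remain the summary for all randomized patients.

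The plan states no hypothesis that one modality tracks MRI better than another, and the correlations are assumed. This also stands: the power figures are illustrative.

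A full cross-table would allow kappa to be derived later, so chance correction is unplanned rather than impossible. True, but 3.10.2 fixes neither the index nor the handling of unmatched levels.

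The continuous analysis has limits of its own. Appendix 1 lets a faint lesion be marked below measurable limit and sets no numerical value for it. Lesions judged to have disappeared are recorded as 0 mm and pile up at −100%. Modalities without a target lesion drop out. The loss of patients alone does not remove the gain: in the table, percent change at n=200 (82, 68, 59, 41%) still exceeds categories at n=300 (43, 34, 28, 19%).

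The separate translational plan might be thought to cover this. Section 3.10 refers translational science objectives to it, with pharmacodynamic, pharmacokinetic and biomarker endpoints, whereas imaging concordance is specified in this SAP. Whether that plan treats MRI enhancement or diffusion separately cannot be seen here.

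**Conclusion.** The point holds as a low-cost improvement to an exploratory analysis. The stated method, raw percentages of categories with unmatched levels, is weaker than the objective and the recorded data allow. Agreement of about 35-50% is expected from unrelated modalities, given equal marginals, the assumed category mixes and MT-cohort rates applied to all patients.

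Three stronger readings are not supported:
- That about half of the agreement is chance. The 0.50 is an agreement rate for unrelated modalities on a responder split at 52%, not a share of observed agreement and not the planned categories.
- That the modalities can hardly be told apart. Those whose correlation with MRI differs by 0.1 mostly could not be separated on categories (roughly 20-45% power against 50-95% at about 300 patients), but clearly different ones often could (61-78%), if a paired test were made.
- That the analysis cannot answer its objective. It answers part of it.

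No primary, secondary or safety conclusion depends on this.

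**What to change.** In SAP 3.10.1 and 3.10.2:

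1. Keep the cross-tables of each local modality against central MRI as the summary in all randomized patients.
2. State how the two category sets map, including Non-CR/Non-PD (which 3.1.4 already labels as SD for patients with non-target lesions only). Show NE, ND and not measurable/not assessed separately, and do not count them as agreement.
3. Add weighted kappa with 95% CI on CR/PR/SD/PD for each local modality against central MRI.
4. Add a supplementary analysis in patients with target lesions on both modalities, with its n beside the category table. On percent change in the sum of diameters from screening to Week 16, report the Bland-Altman mean difference with limits of agreement and a concordance correlation with 95% CI. State the value used for lesions below measurable limit and a sensitivity analysis for it.
5. Give the rank correlation of percent change in diameters with percent change in central MRI enhancing volume. Volume is on another scale, so correlation rather than absolute agreement is the right summary.
6. Say where MRI enhancement and diffusion metrics are handled, or that they are left out of the concordance analysis.

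The cost is SAP wording and a few tables and plots from data already recorded. The downside is that the continuous analysis runs on a selected subset.
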